**6.0 Measurement of Effect**

Screening colonoscopy completion status (in medical charts) six months after the patient expressed informed consent to participate in the study will be the proxy for efficacy of the e-Motivación app in improving screening colonoscopy uptake among Latinos. If the medical chart does not report that a colonoscopy was completed, the colonoscopy will be documented as "not completed". This decision is informed by a study that we have conducted with a similar sample, where less than 10 out of 900+ participants reported completing the colonoscopy at a different hospital.

**6.1 Antitumor Effect- Solid Tumors**

N/A

**6.2 Antitumor Effect- Hematologic Tumors**

N/A

**6.3 Safety/tolerability**

N/A

**7.0 ADVERSE EVENTS**

---

## 7.1 Experimental Therapy

N/A

## 7.2 Adverse Event Monitoring

Adverse event data collection and reporting, which are required as part of every clinical trial, are done to ensure the safety of Subjects enrolled in the studies as well as those who will enroll in future studies. Adverse events are reported in a routine manner at scheduled times during a trial. Additionally, certain adverse events must be reported in an expedited manner to allow for optimal monitoring of patient safety and care.

All patients experiencing an adverse event, regardless of its relationship to the study, will be monitored until:

- the adverse event resolves or the symptoms or signs that constitute the adverse event return to baseline;
- any abnormal laboratory values have returned to baseline;
- there is a satisfactory explanation other than the study for the changes observed; or
- death.

## 7.3 Definitions

### 7.3.1 Definition of Adverse Event

An adverse event (AE) is any untoward medical occurrence in a patient receiving study treatment and which does not necessarily have a causal relationship with this treatment. An AE can therefore be any unfavorable and unintended sign (including an abnormal laboratory finding), symptom, or disease temporally associated with the use of an experimental intervention, whether or not related to the intervention.

### 7.3.2 Severity of Adverse Events

The severity of an AE is graded as follows:

Mild (grade 1): the event causes discomfort without disruption of normal daily activities.

Moderate (grade 2): the event causes discomfort that affects normal daily activities.

Severe (grade 3): the event makes the patient unable to perform normal daily activities or significantly affects his/her clinical status.

Life-threatening (grade 4): the patient was at risk of death at the time of the event.

Fatal (grade 5): the event caused death.

### 7.3.3 Serious Adverse Events

A “serious” adverse event is defined in regulatory terminology as any untoward medical occurrence that:

#### 7.3.3.1 Results in death.

If death results from (progression of) the disease, the disease should be reported as event (SAE) itself.

**7.3.3.2** Is life-threatening.  
(the patient was at risk of death at the time of the event; it does not refer to an event that hypothetically might have caused death if it were more severe).

**7.3.3.3** Requires in-patient hospitalization or prolongation of existing hospitalization for  $\geq 24$  hours.

**7.3.3.4** Results in persistent or significant disability or incapacity.

**7.3.3.5** Is an important medical event  
Any event that does not meet the above criteria, but that in the judgment of the investigator jeopardizes the patient, may be considered for reporting as a serious adverse event. The event may require medical or surgical intervention to prevent one of the outcomes listed in the definition of "Serious Adverse Event".

#### **7.4 Steps to Determine If an Adverse Event Requires Expedited Reporting**

Step 1: Identify the type of adverse event using the aforementioned scale (7.3.2).

Step 2: Grade the adverse event using the aforementioned scale (7.3.2).

Step 3: Determine whether the adverse event is related to the study protocol  
Attribution categories are as follows:

- Definite – The AE is *clearly related* to the study.
- Probable – The AE is *likely related* to the study.
- Possible – The AE *may be related* to the study.
- Unrelated – The AE is clearly NOT related to the study.

Note: This includes all events that occur within 30 days of the last participation of patient in the study. Any event that occurs more than 30 days after the last participation and is attributed (possibly, probably, or definitely) to the agent(s) must also be reported accordingly.

Step 4: Determine the prior experience of the adverse event.

Expected events are those that have been previously identified as resulting from administration of the intervention.

#### **7.5 Reporting Requirements for Adverse Events**

##### **7.5.1 Expedited Reporting**

- The Principal Investigator must be notified within 24 hours of learning of any serious adverse events, regardless of attribution, occurring during the study or within 30 days of the last participation of patient in the study.
- The IRB/PPHS must be notified within 5 business days of "any unanticipated problems involving risk to subjects or others" (UPR/UPIRSO).

The following events meet the definition of UPR

- a. Any new information that indicates a new or increased risk, or safety issue (e.g., interim analysis, safety monitoring report, publication, updated sponsor safety report), that indicates an unexpected change to the risk/benefit ratio for the research.

- b. Protocol deviation or violation that harmed subjects or others or that indicated subjects or others might be at increased risk of harm.
- c. Complaint of subject that indicates subjects or others might be at increased risk of harm or at risk of a new harm
- d. Any breach in confidentiality that may involve risk to the subject or others.
- e. Any harm experienced by a subject or other individual that in the opinion of the investigator is unexpected and at least probably related to the research procedures.

#### 7.5.2 Routine Reporting

All other adverse events- such as those that are expected, or are unlikely or definitely not related to the study participation- are to be reported annually as part of regular data submission.

#### 7.6 Unblinding Procedures

N/A

#### 7.7 Stopping Rules

N/A

### 8.0 DRUG INFORMATION

#### 8.1

N/A

### 9.0 CORRELATIVES/SPECIAL STUDIES

#### 9.1 Sample Collection Guidelines

N/A

#### 9.2 Assay Methodology

N/A

#### 9.3 Specimen Banking

N/A

### 10.0 STATISTICAL CONSIDERATIONS

#### 10.1 Study Design/Study Endpoints

This pilot study is a behavioral research Randomized Control Trial. A previously used English/Spanish questionnaire is administered to assess demographics and medical history of participants. Stratified randomization (per language, English or Spanish) assigns participants to either the e-Motivación condition arm or control arm.

Participants in both groups will be asked to complete their respective tasks on their personal device of choice (going through the e-Motivación App or watching the general health informative video). To determine colonoscopy completion status, patients' medical charts are to be reviewed six months following patient's consent to participate in the study.

---

## 10.2 Sample Size and Accrual

The sample includes 80 participants: 40 in the e-Motivación condition arm and 40 in the control arm. Based on previous studies, this sample will provide a large enough sample to determine the effect of the intervention. We also expect the ratio of male to female participation to be 4 to 6.

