## STUDY SCHEMA

**STUDY SUMMARY**

Title	e-Motivación: Developing and Pilot Testing an App to Improve Latinos' Screening Colonoscopy Rates: Aim III
Short Title	N/A
Protocol Number	IRB-18-00344
Phase	N/A
Methodology	Pilot Randomized Control Trial
Study Duration	9 months to conduct pilot study, 6 months to analyze pilot study data and disseminate results.
Study Center(s)	Single-center
Objectives	To begin to examine the efficacy of the e-Motivación app for improving screening colonoscopy uptake among Latinos (results of the pilot study will inform power calculations for a future randomized clinical trial that will formally test the efficacy of the app).
Number of Subjects	80 subjects total (N=40 in control group, N=40 in condition group)
Diagnosis and Main Inclusion Criteria	
 
1. Self-identified as Latino,a,x
 
2. English or Spanish-speaking
 
3. Received a physician referral for a screening colonoscopy
 
4. Has access to a tablet, smartphone, or computer with working internet
 

Study Product(s), Dose, Route, Regimen	N/A
Duration of administration	N/A
Reference therapy	N/A
Statistical Methodology	Contingency tables and t-tests will be performed to determine any differences between the two groups. Using a p value of $\leq 0.15$ , any consistent pattern of correlation for any of the covariates would suggest their inclusion in the primary data analysis model. Effect size estimate: Logistic regression analyses will be used to evaluate an estimate of the efficacy. The model will include any covariates that differentiate the intervention and control groups. The effect size of the treatment group will be used as an indicator to inform power calculations for a future RCT. The power calculations will inform the appropriate sample size needed for the RCT.

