eliminating errors in data entry and maximizing data security. **(3) Tailored by Language:** E-health interventions can be programmed to be offered in multiple languages (e.g., Spanish and English) to address a wide range of patient populations.

**e-MI to Improve Latinos' Screening Colonoscopy Uptake.** Despite the strong promise of MI for improving screening colonoscopy uptake, and the advantages of e-MI, no study to date has examined the efficacy of e-MI to improve Latinos' screening colonoscopy uptake. This study pilot tests an e-MI intervention, e-Motivación (e-Motivation), to help improve Latinos' screening colonoscopy uptake. This line of research will increase our understanding of efficacious interventions to improve Latinos' CRC screening rates. It will also provide power calculations for a future RCT that will formally examine the efficacy of the e-Motivación app for improving Latinos' screening colonoscopy uptake. This program of research can help increase Latinos' colonoscopy uptake and, in doing so, reduce CRC screening disparities.

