## 2.0 STUDY OBJECTIVES

### 2.1 Primary Objectives

2.1.1 To obtain an estimate of the efficacy of the e-Motivación app for improving screening colonoscopy uptake among Latinos  
[For details, please see section 5.2.2; a detailed flowchart of the App is attached – please see Appendix B]

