## 10.3 Data Analyses Plans

*Analyses of covariates:* Due to the use of randomization, significant baseline differences (e.g., gender, age) between condition and control groups are not expected. However, contingency tables and t-tests will be performed to determine any differences between the two arms. Using a  $p$  value of  $\leq 0.15$ , any consistent pattern of correlation for any of the covariates would suggest their inclusion in the primary data analysis model.

*Effect size estimate:* Logistic regression analyses will be used to evaluate an estimate of the efficacy. The model will include any covariates that differentiate the intervention and control groups. The effect size of the treatment group will be used as an indicator to inform power calculations for a future RCT. The power calculations will inform the appropriate sample size needed for the RCT.

*Missing data:* The e-Motivación app is a one-time intervention and the questionnaire to assess demographics and medical history of participants will be conducted as an interview. Therefore, we anticipate minimal missing data.

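### Section 10.2 says 40 per arm is enough to determine the effect; the stated aim is only an estimate, and under plausible assumptions its 95% CI would be about ±15 to ±22 percentage points

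*Combined protocol and SAP*

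**What the plan says.** Section 10.2 sets 40 participants per arm and justifies this in one sentence: "Based on previous studies, this sample will provide a large enough sample to determine the effect of the intervention". It does not name the earlier studies and gives no calculation.

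The rest of the document claims less:

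- Section 2.1, the only objective: "To obtain an estimate of the efficacy of the e-Motivación app for improving screening colonoscopy uptake among Latinos".
- Study Summary, Objectives: "results of the pilot study will inform power calculations for a future randomized clinical trial that will formally test the efficacy of the app".
- Section 1.4: "It will also provide power calculations for a future RCT that will formally examine the efficacy of the e-Motivación app".
- Section 10.1: "This pilot study is a behavioral research Randomized Control Trial".
- Section 10.3: "Logistic regression analyses will be used to evaluate an estimate of the efficacy".

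Section 10.3 also says what the result is for: "The effect size of the treatment group will be used as an indicator to inform power calculations for a future RCT", followed by "The power calculations will inform the appropriate sample size needed for the RCT". It does not mention a confidence interval.

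**The concern.** Section 10.2 is out of step with the other sections. They describe a pilot estimate with the formal test to follow; 10.2 says the pilot is already large enough to settle the effect, and offers nothing to support that.

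Two things are at stake. First, a reader who relies on 10.2 could take a non-significant pilot result as evidence that the app does not work. Second, the pilot's effect size feeds the sample size of the next trial. If its uncertainty is not stated and carried forward, that trial could be far too small, or could be judged infeasible because the required number looks too large.

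**Working it through.** **The plan's own figure.** There is nothing to reproduce, because 10.2 gives no inputs. As a check, I looked for 80% power (two-sided 5%) using the only two effects quantified in Section 1.1. OR 1.6 needs 288-520 per arm, and OR 2.6 needs 70-151 per arm, over control rates of 30-80%. Treating d = 0.53 as a continuous effect needs 56 per arm; 40 per arm gives 66% power two-sided or 77% one-sided. None of these leads to 40 per arm.

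**Inputs**

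- n = 40 per arm (10.2); binary completion at six months (2.4); logistic regression (10.3).
- OR 1.6 (CI 0.9-3.0): earlier trial of motivational interviewing for colorectal screening (1.1).
- d = 0.53: meta-analysis of motivational interviewing for health behaviours (1.1). Converted by exp(0.53 × π/√3) = 2.615, written as 2.6 below.
- Assumed, because the protocol does not give them: control completion 30-80%, two-sided 5%, unadjusted comparison. The protocol adopts neither effect as a planning value.

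**Formulas.** With control rate p1 and p2 = OR·p1/(1 − p1 + OR·p1):

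- Half-width for the difference = 1.96 × √[p1(1−p1)/40 + p2(1−p2)/40].
- OR limits = OR × exp(±1.96·SE), with SE = √[1/(40·p1(1−p1)) + 1/(40·p2(1−p2))].

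**Worked case: control 50%, OR 1.6.** p2 = 0.8/1.3 = 0.615. Half-width = 1.96 × √(0.00625 + 0.00592) = 21.6 points, against a true difference of 11.5 points. SE = √(0.1000 + 0.1056) = 0.4535, so the OR limits are 1.6 ÷ 2.43 = 0.66 and 1.6 × 2.43 = 3.89, a ratio of 5.9.

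**All scenarios.** Power and the chance of an observed difference of zero or worse come from exact enumeration of the two binomials, using the chi-square test.

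| OR | Control | True difference (points) | Half-width (points) | OR 95% CI | Ratio of limits | Power | P(observed difference ≤ 0) |
|---|---|---|---|---|---|---|---|
| 1.6 | 30% | 10.7 | 20.8 | 0.63-4.03 | 6.4 | 17% | 19% |
| 1.6 | 40% | 11.6 | 21.7 | 0.66-3.88 | 5.9 | 19% | 17% |
| 1.6 | 50% | 11.5 | 21.6 | 0.66-3.89 | 5.9 | 19% | 18% |
| 1.6 | 60% | 10.6 | 20.7 | 0.63-4.05 | 6.4 | 17% | 19% |
| 1.6 | 70% | 8.9 | 19.0 | 0.58-4.42 | 7.6 | 15% | 22% |
| 1.6 | 80% | 6.5 | 16.3 | 0.49-5.27 | 10.9 | 12% | 26% |
| 2.6 | 30% | 22.8 | 21.0 | 1.04-6.55 | 6.3 | 56% | 2% |
| 2.6 | 40% | 23.5 | 21.3 | 1.06-6.45 | 6.1 | 59% | 2% |
| 2.6 | 50% | 22.3 | 20.8 | 1.03-6.63 | 6.4 | 55% | 2% |
| 2.6 | 60% | 19.7 | 19.6 | 0.97-7.09 | 7.3 | 48% | 3% |
| 2.6 | 70% | 15.9 | 17.8 | 0.85-8.00 | 9.4 | 41% | 5% |
| 2.6 | 80% | 11.3 | 15.2 | 0.68-10.03 | 14.7 | 31% | 10% |

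**Consequence for the next trial.** Take control completion of 50% as known, and size the next trial for 80% power, two-sided 5%, with the pooled two-proportion formula. The quartiles of the pilot OR are OR × exp(±0.674·SE).

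| True OR | Pilot OR at 25th / 50th / 75th percentile | Next trial, per arm | True power if sized on the 75th percentile |
|---|---|---|---|
| 1.6 | 1.18 / 1.60 / 2.17 | 2,336 / 290 / 110 | 41% |
| 2.6 | 1.90 / 2.62 / 3.60 | 159 / 74 / 44 | 58% |

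Over control rates of 30-80%, the last column runs from 37% to 41% at OR 1.6 and from 56% to 58% at OR 2.6. One pilot in four would give an estimate at or above that quartile.

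**The case against.** The strongest reply is that *determine* is used loosely. The protocol speaks elsewhere of determining completion status and of determining differences by t-tests, so in 10.2 the word may only mean obtaining an effect size. The surrounding sections say plainly that this is a pilot, and a pilot needs no formal power. That limits the harm, and N = 80 itself is not at fault. The claim that the sample is large enough still has no support on that reading: no precision is stated, and OR limits 6 to 15 times apart do not fix an effect.

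A second reply is that the inputs are mine. The unnamed previous studies might support a larger effect, and Section 1.1 cites a review reporting larger effects of motivational interviewing in minorities. It is fair that 1.6-2.6 is not the protocol's own range. But even at OR 3.5, exact power stays just below 80% at its best (control 30-40%), and the OR limits still differ at least 6-fold. A control rate below my range does not help either: at 10%, the half-width is 14.5 points at OR 1.6 and 15.9 at OR 2.6, while the true differences shrink to 5.1 and 12.4 points.

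Third, the planned model may be covariate-adjusted, and 10.3 calls the effect size only an indicator; it neither confines planning to the point estimate nor rules out a CI. Both points stand. My figures are for the unadjusted comparison, and the power loss in the next trial is conditional on sizing it from the point estimate alone. Nothing in 10.3 guards against that use.

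**Conclusion.** The concern holds. Section 10.2 claims a capability that the design does not have and that the other sections do not claim. Read as estimation, 40 per arm gives a 95% CI of about ±15 to ±22 points and OR limits about 6 to 15 times apart. At OR 1.6 the half-width is roughly twice the true difference or more. At OR 2.6 the two are similar for control rates of 30-60%, and the half-width is the larger at 70-80%. Read as testing, power is 12-19% or 31-59%.

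The mismatch between sections and the missing justification need no assumptions. The sizes rest on control completion of 30-80%, a true OR of 1.6 or 2.6, two-sided 5% and no covariate adjustment. The statement should be corrected, but the pilot can run as designed.

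**What to change.** In 10.2, replace the sentence with text such as:

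> The sample of 40 per arm was chosen for a pilot. Assuming control completion of 30-80% and a true OR between 1.6 and 2.6, the expected 95% CI for the difference in completion is about ±15 to ±22 percentage points, and the CI limits for the OR differ by a factor of about 6 to 15. The pilot is not powered to determine efficacy, and a non-significant result will not be read as evidence of no effect.

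If the investigators have an expected control rate or effect from the previous studies, they should cite those studies and put those values in place of the assumed ranges.

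In 10.3, add:

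> The treatment effect will be reported with its 95% CI. The CI, not only the point estimate, will be used in the power calculation for the future RCT, by showing the required sample size at the point estimate and across the part of the CI that favours the app.

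The cost is a few sentences, with no added patients and no change to N, endpoint or procedures. The stated capability becomes less favourable, and the future trial may be planned larger than the point estimate alone would suggest.

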## 10.3 Data Analyses Plans

*Analyses of covariates:* Due to the use of randomization, significant baseline differences (e.g., gender, age) between condition and control groups are not expected. However, contingency tables and t-tests will be performed to determine any differences between the two arms. Using a  $p$  value of  $\leq 0.15$ , any consistent pattern of correlation for any of the covariates would suggest their inclusion in the primary data analysis model.

*Effect size estimate:* Logistic regression analyses will be used to evaluate an estimate of the efficacy. The model will include any covariates that differentiate the intervention and control groups. The effect size of the treatment group will be used as an indicator to inform power calculations for a future RCT. The power calculations will inform the appropriate sample size needed for the RCT.

*Missing data:* The e-Motivación app is a one-time intervention and the questionnaire to assess demographics and medical history of participants will be conducted as an interview. Therefore, we anticipate minimal missing data.

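### Baseline covariates enter the primary model through chance differences between arms at p ≤ 0.15, and the language stratum is not assigned to the model

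*Combined protocol and SAP*

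**What the plan says.** Section 10.3 begins by noting that "Due to the use of randomization, significant baseline differences (e.g., gender, age) between condition and control groups are not expected". It then plans contingency tables and t-tests between the arms and, at a threshold of p ≤ 0.15, states that "any consistent pattern of correlation for any of the covariates would suggest their inclusion in the primary data analysis model". Under the effect-size paragraph it adds: "The model will include any covariates that differentiate the intervention and control groups". The Study Summary repeats the rule: "Contingency tables and t-tests will be performed to determine any differences between the two groups".

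No closed list of candidate covariates is given, and no coding. Gender and age appear only as examples.

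On design, Section 10.1 says "Stratified randomization (per language, English or Spanish) assigns participants" to the two arms, and Section 10.2 sets "40 in the e-Motivación condition arm and 40 in the control arm". Neither Section 10.3 nor the Study Summary places language in the model. The method of building the stratified lists (blocked or not, block size) is not stated.

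The sole objective in Section 2.1 begins "To obtain an estimate of the efficacy of the e-Motivación app". On how the result is used, Section 10.3 says: "The effect size of the treatment group will be used as an indicator to inform power calculations for a future RCT".

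**The concern.** A covariate earns a place in the outcome model by predicting the outcome, or because the randomisation was stratified on it. The p ≤ 0.15 screen measures neither. It compares randomised arms, so anything it flags is chance imbalance, as the plan's own opening remark implies. Three consequences follow.

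- The adjustment set differs from one hypothetical repeat of the trial to the next. With a logistic model, the meaning of the odds ratio shifts with it.
- Irrelevant covariates that enter by chance add variance to an estimate from 80 people.
- The one factor with a design reason to be in the model, language, has no assured route in. Stratification may balance it so well that the screen cannot select it.

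The estimate is the trial's only objective and feeds the sizing of the next trial, so a stable and predefined estimand is worth having.

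**Working it through.** **Inputs.** From the documents: threshold 0.15 (Section 10.3, Study Summary); 80 patients, 40 per arm (10.2); stratification by language (10.1); 16 main questionnaire items (5.2.1), some of them fixed or nearly fixed by eligibility, such as referral; and an odds ratio of 1.6 from the earlier motivational-interviewing trial in colorectal screening (1.1), the only odds ratio in the documents. Assumed: number and independence of candidates, language share, block size, completion rate, prognostic strengths. The plan has no figure of its own to reproduce here, because 0.15 is a choice and no inputs are given for N = 80.

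**1. Chance entry.** With k independent candidates, P(at least one enters) = 1 − 0.85^k. This gives 0.728 (k = 8), 0.858 (12), 0.879 (13) and 0.926 (16). The expected number entering is 0.15k: 1.8 at k = 12 and 2.4 at k = 16.

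**2. Does language enter?** Exact enumeration, Pearson chi-square at p ≤ 0.15, smaller language group of 16, 24, 32 or 40:

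| List construction | Uncorrected | Continuity-corrected |
|---|---|---|
| Simple randomisation within strata | 0.164 / 0.151 / 0.158 / 0.146 | 0.085 / 0.094 / 0.093 / 0.093 |
| Only the 40:40 total fixed | 0.161 / 0.222 / 0.110 / 0.117 | 0.048 / 0.087 / 0.110 / 0.117 |

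With blocks, the worst case comes from incomplete last blocks.

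- Blocks of 4, language groups of 18 and 62: splits 10:8 and 30:32 give χ² = 80 × (10×32 − 8×30)² / (18×62×40×40) = 0.287, p = 0.592.
- Blocks of 8, groups of 20 and 60: splits 12:8 and 28:32 give χ² = 80 × 160² / (20×60×40×40) = 1.067, p = 0.302.

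For blocks of 6 the smallest p is 0.529. These are the minima when the smaller group is 16 or more. With any of these block sizes language cannot enter unless the smaller group is under 5 of 80.

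**3. Precision.** Simulation with 10,000 replicates per row, n = 80, 40% in one language, 12 independent non-prognostic candidates besides language (2 continuous, 4 binary, 6 with 4–5 levels), true OR 1. Ratios are variances of the log OR, taken over replicates where all models are estimable. A fit counts as failed if any coefficient lacks a finite maximum-likelihood estimate.

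| Lists, completion, coding | Rule ÷ (arm + language) | Rule ÷ three fixed covariates | (Arm + language) ÷ unadjusted | Three fixed ÷ unadjusted | Failed rule fits | Type I error: rule, unadjusted |
|---|---|---|---|---|---|---|
| Blocks of 4, 50%, one df | 1.11 | 1.02 | 1.03 | 1.12 | 0 | 0.055, 0.063 |
| Blocks of 4, 50%, dummies | 1.29 | 1.19 | 1.03 | 1.12 | 174 | 0.054, 0.056 |
| Blocks of 4, 75%, one df | 1.12 | 1.02 | 1.03 | 1.13 | 37 | 0.045, 0.044 |
| Blocks of 4, 75%, dummies | 1.27 | 1.16 | 1.03 | 1.13 | 1,059 | 0.044, 0.047 |
| Simple, 50%, one df | 1.13 | 1.04 | 1.04 | 1.14 | 0 | 0.051, 0.050 |
| Simple, 50%, dummies | 1.28 | 1.17 | 1.05 | 1.15 | 191 | 0.055, 0.054 |

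Arm plus language failed in at most 3 of 10,000 fits. The unadjusted SD of the log OR was 0.458–0.466 at 50% completion and 0.546–0.548 at 75%.

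**4. Shift in what the odds ratio means.** Take a conditional OR of 1.6, 50% control completion and one omitted binary covariate of 50% prevalence with OR 2. Control logits are ±0.347 (mean risk 0.500). Treated logits are 0.470 ± 0.347, giving risks 0.694 and 0.531 (mean 0.612). The marginal OR is 0.612/0.388 = 1.58. With one covariate of OR 3 it is 1.55, and with three of OR 3 it is 1.48. On the log scale the shift runs from ln(1.6/1.578) = 0.014 to ln(1.6/1.479) = 0.079, small beside an SD of about 0.46.

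**5. Power at OR 1.6.** With 4,000 replicates, blocks of 4, 50% completion and previous colonoscopy given a log OR of 1.0, rejection under the rule, arm + language and unadjusted was 0.149, 0.166, 0.166 (one df) and 0.165, 0.185, 0.184 (dummies). The Monte Carlo SE is 0.006.

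A second simulation used 12 continuous candidates, one of them prognostic (log OR 0.5 or 1.0 per SD), and a language log OR of 0.8. The rule-selected log OR differed from the unadjusted one by more than 0.2 in 19% to 24% of trials. At a log OR of 1.0 per SD, rejection at OR 1.6 was 0.126 under the rule, 0.149 unadjusted and 0.160 with language and the prognostic covariate fixed in advance.

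**The case against.** **The wording is soft.** Section 10.3 says only that a pattern would point towards inclusion, and does not say correlation with what. Read alone, that could mean correlation with the outcome. But the tests just before it compare the arms, and "The model will include any covariates that differentiate the intervention and control groups" is unconditional, so the arm-against-arm reading stands.

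**The entry figures lean high.** They assume many independent candidates, each entering at exactly 0.15. With assumed pairwise correlation of 0.2–0.4, the chance of at least one entry is 63–70% (k = 8), 75–83% (k = 12) or 83–90% (k = 16). If every item entered at about 9%, as with a continuity-corrected test, 1 − 0.91^k gives 53%, 68%, 71% and 78% for k = 8, 12, 13 and 16. This stands as a caveat, but chance entry remains more likely than not.

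**Omitting language does no demonstrated harm.** Adding it gained no power in step 5 and cost 3–5% in variance where it was non-prognostic. This also stands. The argument for language is that the analysis should follow the randomisation, not that a loss has been shown.

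**The variance penalty depends on coding.** With one-df coding the rule is only 2–4% worse than a fixed three-covariate set. The upper figures need multi-level dummies, which the plan does not prescribe, though it does not rule them out either. The power differences are also small: the unadjusted result itself moved from 0.166 to 0.184 between runs, although comparisons within a run point the same way.

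**The rule uses baseline data only and is written in advance.** That is true, and it protects type I error. However, the soft wording and the missing list and coding leave choices open while completion status is being reported weekly to the investigator (Section 11.5.1).

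**Conclusion.** The concern holds and is minor. The plan lets chance imbalance decide what the primary model adjusts for and does not assign the stratification factor to it.

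- At least one covariate enters by chance in 73–93% of trials with 8–16 independent candidates, and less often if candidates are correlated or a conservative test is used.
- Language enters in about 5–22% of trials with unblocked lists, depending on list construction and test. With blocks of 4, 6 or 8 it does not enter unless one language group is very small.
- With non-prognostic covariates, the variance of the log OR is 11–29% above arm plus language. Failed fits range from none to 10.6%.

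There is no type I inflation, the non-collapsibility shift is small, and this is not a threat to validity. Confidence is high on what the text says. The magnitudes are illustrative, because they rest on assumed candidate numbers, coding, completion rates and prognostic strengths.

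**What to change.** Delete the p ≤ 0.15 entry rule from Section 10.3 and the Study Summary, and keep baseline comparisons as description only. State the primary logistic model as arm plus language stratum, included whatever the baseline table shows. Optionally add one or two items already collected and judged prognostic, for example age and previous colonoscopy, with their coding written down. Their prognostic value is an assumption, since the documents do not state it. Report the unadjusted odds ratio with its confidence interval alongside.

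Settle this before outcome data are seen: Section 5.4 starts chart review in months 7–9.

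The cost is a paragraph of wording and one to three degrees of freedom. No new data or patients are needed. If the covariates prove unprognostic, the variance of the log OR is 3–5% above unadjusted for arm plus language and 12–15% above with three covariates. The gain in power is over the current rule, not over an unadjusted analysis.
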